1. LIST OF ABBREVIATIONS

ABG Arterial blood gas
AE Adverse event

ALC Absolute Lymphocytic Count
ALT Alanine aminotransferase

aPTT Activated partial thromboplastin time
ARDS Acute respiratory distress syndrome

AST Aspartate aminotransferase

BUN Blood urea nitrogen
CCBB Carolinas Cord Blood Bank

COVID Coronavirus (COVID-19) or SARSoCoV-2, 2019 Novel Coronavirus, nCov

CRP C-reactive protein

CT Computerized tomography

CT CAE Common Terminology Criteria for Adverse Events

DSMB Data Safety Monitoring Board

ECMO Extracorporeal membrane oxygenation

ESR Erythrocyte sedimentation rate FDA Food and Drug Administration

GCS Glasgow coma scale

hCT-MSC Human cord tissue mesenchymal stromal cells

HLA Human leukocyte antigen
INR International normalized ratio
LAR Legally Authorized Representative

LDH Lactic acid dehydrogenase
MAP Mean arterial pressure
MSC Mesenchymal stromal cells
NCI National Cancer Institute

PaO2/FiO2 arterial oxygen partial pressure/fractional inspired oxygen

PCR Polymerase chain reaction
PEEP Positive end expiratory pressure

pH power of hydrogen, refers to acidity or alkalinity

PT Prothrombin time

RT-PCR reverse transcription-polymerase chain reaction

UOP Urinary output SAE Severe adverse event

SARS-CoV-2 Severe acute respiratory syndrome

WBC White blood count

2. PROTOCOL SYNOPSIS

This is a 50 patient, Phase 1/2a multi-center pilot study to test the safety and to describe the preliminary efficacy of intravenous administration of allogenic human cord tissue mesenchymal stromal cells (hCT- MSC) as an investigational agent, under U.S. INDs 19968 (Duke) and 19937 (U Miami) to patients with acute respiratory distress syndrome (ARDS) due to COVID-19 infection (COVID-ARDS). Patients will be eligible for treatment with 3 daily consecutive doses of hCT-MSC at 1 million cells/kg (max dose 100 million cells) in the phase 1 portion of the study or a fixed dose of 100 million cells daily x 3 days, 12-36 hours apart in the phase 2 portion of the study, if they have a

Confidential Page 8 of 32

confirmed diagnosis of COVID-19 and meet clinical and radiographic criteria for ARDS. The primary endpoint is short-term safety of hCT-MSC infusions given on this schedule. The key secondary endpoints are 28 day survival, an increase in PaO2/FiO2 ratio by 50% at 96 hours, days to hospital discharge to home or rehab, and number of days requiring mechanical or non-invasive ventilation or high flow nasal cannula.

The study will be executed in two phases. The first 10 consecutive patients will all receive investigational product. The second part of the study is a randomized, controlled trial in 40 additional patients. The overall aim of the study is to establish safety and to gain critical information as to whether patients with COVID-ARDS will benefit from MSC infusions. Results from the first 10 patients will be compared with concurrent outcomes utilizing standard of care treatments in participating hospitals and in published reports in the medical literature. Results from the additional 40 patients will be analyzed as a randomized placebo control trial. The trial is relying on focused eligibility of the participants (patients with ARDS), single cohort with short trial time (4 weeks), and simple assessment of clinical outcome (survival, improvement of ARDS). This is a sequential design in the sense that after the first 10 patients are evaluated a decision will be made by the PIs and the Data Safety Monitoring Board whether to proceed with the exploratory randomized portion of the study.

The MSCs are manufactured from allogeneic cord tissue donated to the Carolinas Cord Blood Bank (CCBB) at Duke University. The CCBB is an FDA licensed public cord blood bank (licensed name DUCORD). Cord tissue is donated by mothers delivering healthy term male babies by Cesarean section, after written informed consent from the newborn infant's mother. Full donor screening and testing is performed in accordance with regulatory requirements (21CFR 1271). The hCT-MSCs will be manufactured in the Marcus Center for Cellular Cures in the Robertson GMP Cell Manufacturing Laboratory and the Clinical Research Cell Manufacturing Program (CRCMP) laboratory, Interdisciplinary Stem Cell Institute (ISCI), Miller School of Medicine, University of Miami. These hCT-MSCs are already being utilized in clinical trials to treat pediatric patients with autism spectrum disorder (IND 17313), cerebral palsy (IND 17921), hypoxic ischemic encephalopathy (IND 17313) and adults with osteoarthritis of the knee (IND18414). To date, over 210 doses of cells have been delivered to patients on these clinical trials with an excellent safety profile. At University of Miami, hCT-MSCs are used in the clinical trial to evaluate cytokine suppression in patients with chronic inflammation due to metabolic syndrome (IND 17324), 12 subjects in the pilot phase of the study had completed the dose without any treatment emergence SAE.

The rationale for using this approach for patients infected with COVID-19 is that ARDS, the rate-limiting complication impacting survival, is caused, at least in part, by a cytokine release syndrome (CRS) which results is severe immune dysregulation. Involved cytokines include IL-6, IL-8, IL-10, THP-1M, TNF-alpha, and others. MSCs have strong anti-inflammatory and immune-modulatory activities without apparent toxicity or further immunosuppression. Approximately 3-5 % of patients with COVID-19 develop ARDS which carries a very high mortality rate (30-60%) due to multi-system organ failure. Effective treatment of ARDS, the most feared complication of COVID-19, may convert the COVID-19 pandemic into a more manageable "flu-like" illness that every American is expected to experience, and most will survive, on an annual basis.

Confidential Page **9** of **32**

3. BACKGROUND AND RATIONALE

3.1. SARS-COVID-19

Infection with systemic acute respiratory syndrome coronavirus 2 (SARS-CoV-2), also known as COVID-19, has led to a global pandemic. Postulated to have originated from a zoological source, this disease is characterized by the hallmark feature of respiratory illness. Currently, transmission is occurring rapidly from human to human with an array of different clinical features ranging from asymptomatic carriers to a frequently fatal acute respiratory distress syndrome requiring intubation and mechanical ventilation.^{2,3,4} Common clinical features include fever, dry cough and dyspnea. However, the majority of patients are asymptomatic or have minimal flu-like symptoms. At this time, diagnosis is confirmed by real time PCR (qPCR) of a respiratory or nasopharyngeal isolate. Chest radiographs may show alveolar or interstitial opacities and CT imaging of the chest typically shows areas of ground glass and/or consolidation. In its most severe form, COVID-19 leads to acute respiratory distress syndrome (ARDS), thought to be due to inflammatory and oxidant injury resulting in increased alveolar permeability and impaired gas exchange.⁵⁻⁸ Other than supportive care, there is no effective treatment for ARDS, and patients commonly die from sepsis or multi organ failure. 9,10 To date, multiple drug regimens have been tested in clinical trials for the treatment of COVID-19 induced ARDS, including Remdesivir (Gilead) which reduced recovery time by 31% and was recently approved by the FDA for emergency use authorization, however drug availability is extremely limited and not routinely clinically available at this time. Other immunomodulators, such as IL-6 inhibitors and anti-malarials have shown conflicting results. However, the use of MSCs offers a unique therapeutic option for patients with ARDS that might shorten time to lung injury resolution. 11,12 Seven patients with COVID-19 infection received 1 x10 6 MSCs/Kg in Shanghai, China with significant improvement in all patients 2 days after infusion.¹³ After treatment, their C- reactive protein and TNF- α decreased, and the over activated cytokine-secreting immune T and NK cells disappeared. There were no adverse effects due to the MSCs infusion. The investigators concluded that MSCs were safe and effective in patients with COVID-19 pneumonia, especially those in critical condition. An additional recent report of a meta-analysis of MSC therapies (all sources) for COVID-ARDS reviewed 9 studies reporting outcomes of 200 participants and showed a favorable safety profile with a trend towards improved X-Ray findings, pulmonary functions, and inflammatory biomarker levels.14

Here we propose the use of Mesenchymal Stromal Cells for treatment of severe infection characterized by ARDS in patients with a confirmed diagnosis of COVID-19.

3.2. RATIONALE FOR TREATMENT PLAN

MSCs from various sources (adipose tissue, bone marrow, and cord tissue) are in clinical trials for patients with a variety of pulmonary conditions including but not limited to pulmonary fibrosis, ¹⁵⁻¹⁷ non- CF bronchiectasis, asthma, bronchopulmonary dysplasia, and acute respiratory distress syndrome (ARDS). ¹⁸ The rationale for this approach is that MSCs have anti-inflammatory properties without apparent toxicity and may provide similar to superior results with less toxicity than conventional pharmaceutical treatments. ¹⁹⁻²⁴ Furthermore, MSCs have been shown to have antimicrobial activities, ²⁵ which, in preclinical models, have been shown to eliminate certain bacteria and mycobacteria from animal, and tissue culture models of cystic fibrosis. Adipose derived MSCs from younger mice have also been shown to have superior activity compared to MSCs from older mice in a chronic mouse model of Bleomycin-induced pulmonary fibrosis. ²⁶ Human MSCs have been found to reduce influenza A H5N1- associated acute lung injury in mice with a direct impact on survival. ²⁷ In another study, 2 patients with severe ARDS were treated with MSCs on a

Confidential Page 10 of 32

compassionate basis at Karolinska Institute, and showed resolution of respiratory, hemodynamic, and multi-organ failure.²⁸ A decrease in multiple pulmonary and systemic markers of inflammation was seen as well as suppression of T-cell responses and induction of regulatory phenotypes in T-cells, monocytes, and neutrophils. Furthermore, a 17 patient group with influenza H7N9 ARDS treated with menstrual-blood derived MSCs in China had substantially lower mortality than the control group of untreated ARDS patients (17.6% versus 54.5% death).²⁹ Ongoing, unpublished work from investigators at the University of Miami and Duke has shown that cord tissue derived MSCs have higher potency compared to bone marrow and adipose derived MSC from young mice and older mice. MSCs also can differentiate into alveolar epithelial cells in vitro, although their capacity to do this in vivo is not known.³⁰ This has led to the hypothesis that MSCs may work through both anti-inflammatory, immune-modulatory, and regenerative mechanisms in vivo.³¹⁻⁴⁰

In this study, we will test the safety and describe the efficacy of human cord tissue derived MSCs (hCT-MSC) in patients with COVID-ARDS. It is hypothesized that COVID-ARDS occurs as a consequence of a cytokine storm (or cytokine release syndrome, CRS) and occurs in ~3-5% of COVID-19 infected patients. Involved cytokines include IL-6, IL-8, IL-10, THP-1M, TNF-alpha, and others. hCT-MSCs have been shown to suppress RNA expression and secretion of these cytokines by macrophages and T-cells in vitro. They also have a higher proliferative capacity than MSCs derived from adult derived bone marrow or adipose tissue. 41 hCT-MSCs, manufactured at Duke in the Robertson GMP Cell Manufacturing Laboratory in the Marcus Center for Cellular Cures, have been tested in 115patients in clinical trials under INDs 17313, 17921 and 18414 over the past 4 years.⁴² Safety profiles have been extremely favorable. We now propose to utilize these cells in a sequential study where part I is a Phase 1 safety study in 10 consecutive adult patients with COVID-ARDS dosing at 1 million cells/kg (max dose 100M cells) given intravenously, daily x 3. The primary endpoint of this study is safety. Key secondary endpoints are 28 days survival, an increase in PaO2/FiO2 ratio by 50% at 96 hours, days to hospital discharge to home, and number of days requiring mechanical ventilation. If safety is demonstrated in this 10 patient cohort, a second phase of this trial will describe the efficacy of hCT-MSCs in an additional cohort of 40 patients who will be randomized in a blinded fashion 2:1:1 to placebo, hCT-MSC manufactured at Duke, or hCT-MSC manufactured at Miami. This randomization plan will yield 20 participants on placebo and 10 in each of the hCT-MSC arms. The two hCT-MSC arms will be pooled for analyses comparing treated patients to placebo.

Phase I, Safety

10 patients
1x10^6/kg patient weight
(max 100x10^6)

Phase II Randomization, Efficacy

Placebo

hCT-MSCs

10 patients
DUKE
Fixed dose 100x10^6

10 patients
UNIVERSITY OF MIAMI
Fixed dose 100x10^6

Confidential Page 11 of 32

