3.3. OBJECTIVES

The Primary Objective of this study is safety of the Investigational Product, hCT-MSCs.

The primary endpoint is safety measured by:

- 1. Incidence of infusion reactions
- 2. Incidence of later reactions attributed to the investigational product Formation of new anti-PRA antibodies

The Secondary Objective of this study is to describe the potential for MSC therapy to favorably alter the course of COVID-ARDS. Endpoints are:

- 1. Time to recovery, defined as discharge from the hospital (alive) or remaining in the hospital without the need for supplemental oxygen or other COVID-related medical care.
- 2. Increase in PaO2/FiO2 ratio by 50% by Day 4 (96 hours after first infusion). PaO2/FiO2 may be calculated from an arterial blood gas or imputed from the SpO2/FiO2 table (Brown, et al. Chest 2016).
- 3. Days to hospital discharge to home
- 4. # of ventilator free days
- 5. # of days requiring O2 support
- 6. Feasibility of accrual to the randomized portion of this study

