4. ENROLLMENT AND WITHDRAWAL

All patients will receive standard ICU monitoring and all available supportive care for their condition, including oxygen, antibiotics, bronchodilators, mechanical ventilation, antibiotics, etc., and any other FDA approved treatment for COVID-19 infection as per treating physician.

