4.1. INCLUSION CRITERIA

- 1. The patient or legally authorized representative (LAR) must have the ability to understand and the willingness to provide a signed and dated informed consent form.
- 2. Age 18 years and over
- 3. The patient agrees to use adequate contraception for the duration of the treatment protocol and for 6 months post treatment.
- 4. Positive RT- PCR testing for COVID-19 nucleic acid using nasopharyngeal swabbing or any other site
- 5. Patient meets ARDS criteria and is on non-invasive or mechanical ventilation or high flow nasal cannula
 - a. bilateral opacities on chest imaging consistent with pulmonary edema

Confidential Page **16** of **32**

- b. A need for positive pressure ventilation or high flow nasal cannula
- c. PaO2/FiO2 ratio ≤ 300 mmHg by arterial blood gas or SpO2/FiO2 imputation.
- d. Infiltrates not fully explained by cardiac failure or fluid overload in the physician's best clinical judgement
- 6. Subjects requiring dialysis as a result of a COVID-19 infection will not be excluded.

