6.1.1. LABORATORY AND CLINICAL EVALUATIONS

- Baseline is at enrollment (within 3 days- excluding COVID-19 PCR test which can obtained within 90 days to avoid repeat testing). Days post infusion are calculated from the first infusion. The "*" signifies that the test results from standard of care testing will be used however, they do not need to be obtained specifically for the study
- Height and weight with baseline physical examination
- Hematology: hemoglobin, hematocrit, platelet count, white blood cell (WBC) count, and WBC differential at baseline, day of infusion, Day 4, Day 7*, and Day 28*
- Coagulation: prothrombin time (PT)/aPTT/INR, D-dimer at baseline, Day 4*, and Day 28*
- Serum chemistry: CRP, ESR, AST, ALT, LDH, total bilirubin, alkaline phosphatase, total protein, albumin, sodium, potassium, chloride, carbon dioxide, calcium, blood urea nitrogen (BUN), creatinine, creatinine clearance and glucose at baseline, day of infusion*, Day 4*, Day 7*, and Day 28*
- Urinalysis*: pH, specific gravity, protein, glucose, ketones, blood, leukocyte esterase, and nitrite at baseline. Microscopy required only to follow-up clinically significant abnormal findings
- Chest x-ray* at baseline, Day 4*, Day 7*, and Day 28*
- ABGs prior, 1-4 hours after, Day 4*, Day 7*, and Day 28*
- COVID-19 PCR at baseline (do not repeat testing if obtained within 90 days of enrollment), day
 4*, 7*, and 28* post treatment
- Donor referral panel at baseline
- HLA typing (high resolution class I and class II) at baseline
- PRA (Anti-HLA antibodies) at baseline and day 28
- PaO2/FiO2 and oxygenation index endpoints (based on invasive or non-invasive mechanical ventilation or high flow nasal cannula use). To be done at Baseline, Day 1, Day 2, Day 4, and if on continued ventilation Day 7, and Day 14. PaO2/FiO2 may be calculated from an arterial blood gas or imputed from the SpO2/FiO2 table (Brown, et al. Chest 2016)
- Day 28 mortality
- Hospital discharge
- Invasive or non-invasive mechanical ventilation-free days and oxygen-free days
- Lung injury severity score (Murray) at Baseline, Day 1, Day 2, Day 4, Day 7, and Day 14. The
 most recent chest x-ray will be used to calculate the Murray score. For patients on pressure
 support mode ventilation, the peak pressure will be used in place of the plateau pressure to
 calculate compliance
- Any laboratory or imaging can be repeated outside the protocol requirements at the discretion of the treating physicians

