9.4 ANALYSIS PLAN

Baseline characteristics of the participants will be summarized by study phase. The proportion of patients with infusion-related reactions and other unexpected product- related adverse reactions will be tabulated descriptively using CTCAE terminology. For Phase II, the time to recovery will be described using Kaplan-Meier plots comparing cumulative incidence in participants randomized to hCT-MSC with placebo. Results will be analyzed two ways: combining the two hCT-MSC arms vs. placebo, and each hCT-MSC arm separately vs. placebo. Other continuous, ordinal and binary outcomes will be analyzed in a similar fashion using appropriate descriptive statistics.

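### The ventilation endpoint has four non-equivalent wordings; two of them ignore high flow nasal cannula, which alone qualifies a patient for entry

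*Combined protocol and SAP*

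**What the plan says.** The endpoint appears in four places of the combined protocol and SAP:

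- Section 2 (synopsis), among the key secondary endpoints: "number of days requiring mechanical or non-invasive ventilation or high flow nasal cannula".
- Section 3.2, in a second list of key secondary endpoints: "number of days requiring mechanical ventilation".
- Section 3.3, secondary endpoint 4: the number "of ventilator free days", with no devices, window or rule for deaths.
- Section 6.1.1, in the list of evaluations: "Invasive or non-invasive mechanical ventilation-free days and oxygen-free days".

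Entry criterion 5 in section 4.1 reads "Patient meets ARDS criteria and is on non-invasive or mechanical ventilation or high flow nasal cannula", so a patient can enter on high flow alone. Section 9.4 neither names nor defines the endpoint. It falls under the general sentence "Other continuous, ordinal and binary outcomes will be analyzed in a similar fashion using appropriate descriptive statistics".

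**The concern.** Two wordings count days on support and two count days free of it, so a good result is a low number in one pair and a high number in the other. High flow counts only in the synopsis. Non-invasive ventilation counts in the synopsis and in section 6.1.1, is not named in section 3.2, and is unspecified in section 3.3.

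High flow is one of the three kinds of support that qualify for entry. Where it does not count, time spent on it leaves no trace in the endpoint. Because section 9.4 makes no choice, an analyst could settle on one wording after seeing the data, and a reader of the report could not tell which one had been planned.

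**Working it through.** The plan gives no figure for ventilation days, so there is nothing of its own to reproduce. The check is to score the same patient under each wording.

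**Inputs.** The wordings are those quoted from sections 2, 3.2 and 6.1.1. The courses are assumed for illustration. All start on high flow (HF), and unless a death is stated, the patient is alive at Day 28 with none of the three kinds of support after the days shown. The free-day wordings state no window; I assume 28 days.

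**Formulas.**
- Synopsis = invasive days + non-invasive days + HF days.
- Section 3.2 = invasive days, or invasive + non-invasive days if mechanical ventilation is read to include both.
- Section 6.1.1 = 28 − invasive days − non-invasive days, and also minus days after death if those are not counted as free.

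| Course | Synopsis, days on | Section 3.2, days on | Section 6.1.1, days free |
|---|---|---|---|
| A. HF days 1–10 only | 10 | 0 | 28 |
| B. HF days 1–3, intubated days 4–15 | 3 + 12 = 15 | 12 | 28 − 12 = 16 |
| C. HF days 1–3, non-invasive days 4–9 | 3 + 6 = 9 | 0 or 6 | 28 − 6 = 22 |
| D. HF days 1–4, dies day 5, never intubated | 4 | 0 | 28 − 24 = 4, or 28 |
| E. HF 5 days, invasive 5, HF 5 | 15 | 5 | 28 − 5 = 23 |
| F. HF for all 28 days | 28 | 0 | 28 |

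Section 3.3 cannot be scored as written. Read as free of invasive ventilation only, it would give course C 28 free days against 22 under section 6.1.1, and course D either 4 or 28.

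**Reading the table.** Courses A and F differ by 28 − 10 = 18 days of high flow. The synopsis wording shows that difference. Section 3.2 gives 0 for both and section 6.1.1 gives 28 for both. Courses B and E show the other side: once a patient who entered on high flow is intubated, days accrue under every wording.

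**Whether the wordings are loose synonyms.** The documents name high flow where they mean to include it: in the synopsis, in entry criterion 5, and in the PaO2/FiO2 item of section 6.1.1. The ventilation-free-days item in that same list omits it. The synopsis and criterion 5 also list non-invasive ventilation beside mechanical ventilation as a separate thing, whereas section 6.1.1 treats it as a form of mechanical ventilation. That is why course C has two possible scores under section 3.2.

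**The case against.** The strongest reply is that high-flow burden is recorded elsewhere. Section 3.3 lists the number "of days requiring O2 support" as its own endpoint, section 6.1.1 adds oxygen-free days, and an inpatient still on high flow at Day 28 has not met the definition of recovery in sections 3.3 and 9.1.2. Separate ventilator and oxygen endpoints can be a coherent design. Much of this stands: the patient in course F would be recorded as doing badly on other endpoints. It does not settle which ventilation endpoint will be reported. Nor do oxygen-support days, which carry no definition, distinguish high flow from low-flow oxygen. If both count, 10 days of high flow plus 5 of low flow gives 15, and so does 4 plus 11.

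It is also fair to say that section 3.3 is a label rather than a rival definition, and that section 6.1.1 may be meant to spell it out. That would reduce the count of wordings but leave the conflict with the synopsis.

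Three stronger readings are tempting and not supported.

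- A reader might infer that a patient enrolled on high flow scores zero under section 3.2 whatever happens. Section 4 provides all patients with supportive care "including oxygen, antibiotics, bronchodilators, mechanical ventilation, antibiotics, etc", and course B scores 12. The zero applies only to patients never escalated to mechanical ventilation.
- A reader might infer that the endpoint cannot show benefit in patients who enter on high flow. Intubation avoided or shortened would register under every wording that can be scored. Only weaning from high flow itself is lost.
- A reader might infer that chance imbalance in baseline support is a defect of the narrow wordings. It can move any support-day count, including the synopsis one, and the documents do not state what share enters on high flow.

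**Conclusion.** The inconsistency is real and should be corrected. For one patient the documents can yield 10 days on support, 0 days on support or 28 free days (course A). A patient who enters on high flow, is never escalated and is alive at Day 28 scores 0 under section 3.2 and the maximum under section 6.1.1, however long high flow lasts.

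The size of the effect on the trial cannot be given. It depends on how many patients enter on high flow and are never ventilated, which is not stated, and the courses above are illustrations. The reach is limited: the primary endpoint is safety, time to recovery is the main efficacy outcome of Phase II, and this endpoint is secondary and summarised descriptively. What is at stake is the meaning of that summary and the room left for selective reporting, not the primary conclusion.

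**What to change.** Use one definition in sections 2, 3.2, 3.3, 6.1.1 and 9.4. Take the device scope from the synopsis (invasive ventilation, non-invasive ventilation or high flow) and one direction. A suitable form is days alive and free of that support to Day 28, with days after death not counted as free. The rule for death is needed because a plain count of days on support rewards early death: course D scores only 4 under the synopsis. Under the proposed form, courses A to F score 28 − 10 = 18, 28 − 15 = 13, 28 − 9 = 19, 28 − 4 − 24 = 0, 28 − 15 = 13 and 28 − 28 = 0. Courses A and F are then separated, and early death no longer looks favourable. Invasive-ventilation-free days can stay as a supplementary summary.

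The cost is wording, plus one check on data capture. Section 8.3 says that patients are followed daily in hospital, but the visit schedule in section 7 has no row for daily support mode, and its oxygen-use row is marked only at Day 90. The sponsor should confirm that the case report form records support mode for each day to Day 28, and add it if it does not.
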